corresponds to the fake device. The Engineer will not reveal this information to any source (investigators, subjects, CRO, or Sponsor) until the final study data analysis is complete and the Post-Study Open-Label phase begins.

Once a subject has signed the informed consent form, the Principal Investigator will contact the Sponsor (via email or phone) who will act as the central source for providing sequential subject procedure group assignment.

SUBJECTS

Subject Sample

Subjects will be males and females aged 18 years or older who have diagnosed diabetic peripheral neuropathy with pain persisting over at least the past three months.

Sample size

There will be 64 qualified subjects enrolled in this clinical study:

32 subjects in the active procedure group
32 subjects in the control procedure group

Rationale for sample size

Based on the following parameters established for the purposes of assessing efficacy of the Erchonia® FX-635™ in this clinical study ...:

- Individual subject success criteria defined as a 30% or greater reduction in self-reported Degree of Pain rating on the 0-100 VAS from baseline to study endpoint evaluation.

N.B.: The clinical relevance of a 30% change in VAS score is explained and supported in the STATISTICAL ANALYSIS PLAN section further along in this protocol document.

- Overall study success criteria of at least a 35% difference between the test device group and the placebo group, comparing the proportion of individual successes in each group.
- It is anticipated that about 55% of subjects in the test device group and about 20% of subjects in the placebo group will meet the individual success criteria, and
- intended application of a two-tailed test with an alpha value of 0.05 and Power of 0.8

...the sample size of 29 subjects per group (test group and the control group, separately) has been determined using the following reference calculator:

Hypothesis Testing: Categorical Data - Estimation of Sample Size and Power for Comparing Two Binomial Proportions in Bernard Rosner's *Fundamentals of Biostatistics*.

For the purposes of sample size calculation, it is anticipated that about one-twentieth of subjects overall may withdraw from the study prior to completion for various reasons. Therefore, the following formula is used to determine the final needed starting sample size for each group:

Final sample size = sample size X $1/(1-d)$; where d = # expected dropouts/# subjects enrolled.

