Records for each subject in this clinical study will be maintained in separate files in a locked filing cabinet at the respective test site. The investigator at the test site will be responsible for ensuring that all records for a subject pertaining to his or her participation in the clinical study are maintained in the subject's file at all times other than when information is being recorded on them.

Copies of all subject case report forms will be made and supplied to Regulatory Insight, Inc. and Erchonia Corporation. Regulatory Insight, Inc. and Erchonia Corporation will maintain these copies in a separate clinical study file that is kept in a locked filing cabinet on their respective premises. The original records will be maintained at the respective test sites.

Subjects' identities will be kept confidential by assigning each subject a subject ID upon acceptance into the study. The subject ID will comprise the investigator's two initials (first and last name initials) and a three-digit number that will be based upon the subject's order of entry into the clinical study. Each test site will be assigned a unique range of numbers. Test site #1 will be assigned numbers 001 to 100. Test site #2 will be assigned numbers 101 to 200, and so on. For example, the eighth subject to be enrolled at test site #2 with Principal Investigator John Black would have a subject ID of JB108. Neither the study Sponsor nor Regulatory Insight, Inc. will receive any additional identifying information about a subject and will therefore have no way of linking a subject ID to a particular subject and his or her results.

MONITORING OF THE CLINICAL STUDY

Monitoring of the clinical study will be according to the applicable protocols and procedures contained within the Erchonia Corporation Clinical Trials Monitoring Plan, CT-003, R3.

STATISTICAL ANALYSIS

PRIMARY EFFICACY OUTCOME MEASURE: CHANGE IN SUBJECT SELF-REPORTED VAS PAIN RATING FROM BASELINE TO STUDY ENDPOINT

Primary efficacy outcome measure for this clinical study will be a statistically significant difference in the proportion of subjects between test and control groups who achieve a clinically meaningful and statistically significant decrease in self-reported VAS pain rating from baseline to study endpoint.

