For this group, the following secondary efficacy outcome measure will be evaluated:

- d) Change in VAS rating across and between all study evaluation time points to study endpoint evaluation within and between treatment groups

- e) Changes in scores on the Neuropathic Pain Symptom Inventory (NPSI) across and between all evaluation points to study endpoint evaluation within and between treatment groups
- f) Differences in the use of rescue pain medication between procedure groups across study duration to study endpoint evaluation.

STATISTICAL METHODS

Efficacy analysis will be according to the intent to treat (ITT) principle by last observation carried forward (LOCF).

Intent to Treat: Subjects will be included in the analysis if they were randomized to study procedure group, had a valid baseline visit including the required Low Back Pain VAS recordings; and received the first study procedure administration.

Last observation carried forward: Missing data will be handled by carrying forward the last observation.

Per-protocol analysis will also be performed for the set of all subjects who were randomized to procedure group and completed the study according to the full protocol.

STATISTICAL ANALYSIS

The primary analysis of efficacy will be through the application of:

- 1) **Fisher's exact test** to compare the proportion of success between the test and the control groups, considering that randomization has been diligently conducted and important covariates between the two groups are well balanced.
- 2) **Parametric ANCOVA model** analysis with the mean change from baseline to study endpoint in foot pain ratings on the VAS as the dependent variable, procedure group as the independent variable of interest and baseline average foot pain VAS rating as a covariate. A two-tailed significance level of 5% will be considered to be statistically significant.

Covariates: The following potential covariate baseline variables will be adjusted, as applicable, through application of an ANCOVA analysis for the continuous variables and linear regression analysis for categorical variables.

- ✓ Baseline VAS rating
- ✓ Baseline NPSI total score
- ✓ Duration of foot pain
- ✓ Time since Diabetes diagnosis
- ✓ Insulin dependent versus non-insulin dependent Diabetes
- ✓ Age
- ✓ Gender

Secondary Measures Analysis

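### Two analyses of different variables are both labelled primary with no order or combination rule, although the hypothesis, success criterion and sample size concern responder proportions only

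*Combined protocol and SAP*

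**What the plan says.** All references are to the combined protocol and SAP.

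- **Statistical Analysis (after Statistical Methods).** The lead-in is "The primary analysis of efficacy will be through the application of", followed by two numbered items. Item 1 is Fisher's exact test on success proportions, on the consideration that "important covariates between the two groups are well balanced". Item 2 is a parametric ANCOVA, "analysis with the mean change from baseline to study endpoint in foot pain ratings on the VAS as the dependent variable", with baseline average VAS as covariate. Item 2 ends: "A two-tailed significance level of 5% will be considered to be statistically significant".
- **Covariates (same subsection).** Seven baseline variables are listed under "The following potential covariate baseline variables will be adjusted, as applicable". No selection rule is given. Test site is not among them, although Randomization says allocation is stratified by site.
- **Primary Efficacy Outcome Measure.** The primary outcome is "a statistically significant difference in the proportion of subjects between test and control groups" in achieving the defined VAS decrease. The overall success criterion (at least a 35-point difference), the null hypothesis and the alternative are all stated for proportions of individual successes.
- **Rationale for sample size.** The calculation uses proportions only: "It is anticipated that about 55% of subjects in the test device group and about 20% of subjects in the placebo group" are expected to succeed, with "intended application of a two-tailed test with an alpha value of 0.05 and Power of 0.8".
- **Secondary Efficacy Outcome Measures and Secondary Measures Analysis.** Change in VAS rating is the first secondary measure for the blinded data set, and continuous secondary measures are to be analysed by ANCOVA.

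**The concern.** VAS change analysed by ANCOVA is secondary in two places and primary in a third, and the third is the section that an analyst will carry out. Nothing there says what happens when the two numbered analyses disagree.

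If they disagree, the report could rest the primary claim on whichever test is significant. The balance clause supplies an argument for setting the Fisher result aside: balance has no definition, no threshold and no stated consequence if it fails. The open covariate list then allows more than one version of the adjusted model.

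The results are meant to support a 510(k) submission, so the test that decides the claim should be beyond argument before unblinding.

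**Working it through.** **1. The plan's own figure.** Inputs from Rationale for sample size: p1 = 0.55, p2 = 0.20, two-sided alpha 0.05, power 0.80. The pooled proportion is (0.55 + 0.20)/2 = 0.375.

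n = [1.96 × √(2 × 0.375 × 0.625) + 0.8416 × √(0.55 × 0.45 + 0.20 × 0.80)]² / 0.35²
= [1.3419 + 0.5372]² / 0.1225 = 3.531 / 0.1225 = 28.8, rounded up to 29.

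This reproduces the stated 29 per group (32 enrolled). The trial was sized for one comparison of proportions at the full 5%, with no allowance for a second primary test.

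**2. Simple bounds for two tests at 5%, either sufficient.** If independent: 1 − 0.95² = 9.75%. Bonferroni bound: 10%. The true figure is lower, because the tests are correlated and Fisher's test is conservative.

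**3. Error of each possible decision rule under no effect, 32 per arm.** Fisher's size comes from full enumeration of the binomial tables. The joint figures come from simulation, 60,000 trials per scenario. Assumptions not in the documents: baseline VAS truncated normal on 50-100 (mean 68, SD 10); percent change normal with SD 20, 30 or 40; common responder rate 20%, 37.5% or 50%.

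| Decision rule | Two-sided type I error |
|---|---|
| Fisher alone | 2.4% (rate 20%), 2.9% (37.5%), 3.3% (50%) |
| ANCOVA alone | about 5% |
| Either at 5% | 6.2-6.7% |
| Both required at 5% | 1.0-1.8% |
| Either, each at 2.5% | 3.1-3.5% |

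Check for one scenario (rate 20%, SD 30): 2.45% + 4.77% − 1.06% = 6.16%, the simulated figure for either test. At 29 per arm, either test gives 5.8-6.1%. Counting only results that favour the active device, either test at 32 per arm gives 3.1-3.4%, against a nominal 2.5%.

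For comparison, an observed difference of at least 35 points in favour of test has probability below 0.2% under no effect at 32 per arm.

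**4. If the model is chosen after seeing the data.** 6,000 trials per scenario, null rate 20%, 32 per arm, covariates assumed to explain 0 to 25% of outcome variance:

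- best of Fisher, baseline-only ANCOVA and seven-covariate ANCOVA: 7.7-9.1%;
- Fisher or the best of all covariate subsets (baseline VAS always kept): 10-14%.

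**5. The balance clause as a fixed rule.** Fisher if balanced, otherwise the seven-covariate ANCOVA, gives 3.1-3.3% under the same assumptions.

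**6. How often the tests would disagree.** 32 per arm, 6,000 trials per scenario, baseline mean 68 and SD 12, percent-change SD 24 or 35 (assumed):

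- 55% vs 20%: ANCOVA significant and Fisher not in 18-19% of trials;
- 40% vs 20%: the same pattern in 30-31%;
- the reverse pattern in at most 2%.

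Under no effect, disagreement is the either figure minus the both figure, for example 6.16% − 1.06% = 5.1%.

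**The case against.** The best defence is that the confirmatory structure is responder-only throughout: expected results, sample size, primary outcome, individual and overall success criteria, and both hypotheses. The ANCOVA has no hypothesis and no success criterion, and VAS change is already listed as secondary. On this view the second numbered item is a labelling slip rather than a second route to success. This largely stands, and it is why the point is a contradiction to remove rather than a demonstrated loss of error control.

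A reader might infer that type I error exceeds 5% as the plan is written. The documents do not support that. It requires an either-test rule, or a model chosen from the data, and no section contains such a rule. No section excludes one either.

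A reader might also infer that the balance clause drives the error up. It does not. The clause reads as a rationale, the baseline variables are recorded before the first procedure, and applied as a fixed rule it keeps error below 5%. What remains is that the plan fixes no such rule and that randomisation already justifies Fisher's test.

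Two further points are fair. The excess with the two listed tests alone is modest, and the larger figures assume a free search over covariates, whereas the numbered ANCOVA already names its one covariate. Disagreement between the tests is also a minority outcome in every scenario simulated. It is, however, almost entirely one-sided, with the ANCOVA in a position to rescue a failed responder test.

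**Conclusion.** The contradiction is in the text and does not depend on any simulation: one subsection makes the ANCOVA of VAS change primary, while the rest of the plan makes the responder comparison the only primary question and VAS change secondary.

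The consequence is conditional. If either test sufficed, error would rise by about 1 to 2 points above 5%. It would rise further only with covariate choice guided by the results. Under the responder hypothesis alone, or with both tests required, there is no inflation. The joint figures rest on assumed baseline and change distributions that the documents do not give; across the ranges tried, the two-test result varied little. The issue should be settled before unblinding, but it is one of wording and pre-specification.

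**What to change.** In the Statistical Analysis subsection:

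1. Name the responder comparison by Fisher's exact test as the single primary analysis, at two-sided 5%.
2. Make the ANCOVA of VAS change the first secondary test, with baseline VAS and test site (the randomisation stratum) as fixed covariates, confirmatory only if the primary test is significant.
3. Delete the balance premise.
4. If a model with the seven listed covariates is wanted, specify it in advance, with all seven, as a sensitivity analysis, and remove the as-applicable qualifier.

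Requiring both tests or splitting alpha would also control error. A 2.5%/2.5% split would lower Fisher's exact power for 55% vs 20% at 32 per arm from 78.3% to 69.1%. The fixed order keeps the full 5% for the test on which the trial was sized.

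The cost is a change of wording, with no effect on sample size, visits or data collection. The downside is that a significant ANCOVA with a non-significant Fisher test could no longer carry a primary claim. Adding site is a design preference consistent with the stratification; the contradiction could be removed without it.

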Final sample size = $29 \times 1/(1-0.083)$

Final sample size = $29 \times 1/0.917 = 29 \times 1.0905 = 31.62$, rounded to 32 subjects per procedure group.

Therefore, a minimum starting sample size of 32 subjects in each group is needed to ensure that sufficient numbers remains at the end of the trial (29 subjects per group) for any significant differences found between groups to be considered statistically valid and representative of the general population being sampled. This results in a total of 64 subjects being enrolled in this study across both study procedure groups.

Recruitment

Subjects will be recruited from among the Principal Investigator's/test site's pool of patients who are currently being treated for, or who are seeking treatment for, diagnosed diabetic peripheral neuropathy, or from response to the following recruitment materials.

a) Flyer

WANTED

**ADULTS WITH DIABETES WITH FOOT PAIN
ONGOING OVER THE LAST 3 MONTHS FOR**

A

**CLINICAL STUDY OF THE EFFECTS OF
LOW LEVEL LASER LIGHT ON
REDUCING FOOT PAIN**

**THIS STUDY INVOLVES TWELVE
LASER LIGHT PROCEDURES
WITH THE ERCHONIA® FX-635™ LASER
OVER SIX WEEKS AT THE TEST SITE.**

**THERE ARE THREE MORE VISITS TO THE TEST SITE
TWO WEEKS, FOUR WEEKS AND THREE MONTHS
AFTER THE LAST LASER LIGHT PROCEDURE.**

FOR MORE INFORMATION PLEASE

CONTACT:

<PI name>
<test site name & location>
<phone # and/or e-mail>

b) Newspaper Ad

Diabetic Foot Pain Research Study

This study is to see if the Erchonia® FX-635™, a non-invasive, investigational device that uses low-level laser light, can help to relieve foot pain in people with diabetes that has been ongoing for at least 3 months.

The study involves fifteen visits to a test site and recording some information at home.

Please contact <PI name> at <test site name & location> at <phone and/or e-mail> for details.

Compensation

A subject will not receive financial or any other form of compensation to participate in this clinical study. However, he or she will also not be charged for the cost of the study procedures with the Erchonia® FX-635™ Laser or for the cost of any other directly-related evaluations or measurements that occur as part of his or her participation in the study.

STUDY PROCEDURE

STUDY TEST BATTERY

The following is a list of the study outcome assessment tools that will be used in this clinical study. For each study phase, the precise tools from this list that will be employed will be specified.

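### The 29 per group said to give 80% power gives about 71% under the planned Fisher's exact test; the enrolled 32 per group gives about 78%

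*Combined protocol and SAP*

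**What the plan says.** Under *Rationale for sample size*, the anticipated success rates are about 55% (test) and about 20% (placebo), with "intended application of a two-tailed test with an alpha value of 0.05 and Power of 0.8". On that basis, "the sample size of 29 subjects per group (test group and the control group, separately) has been determined" from a textbook section titled "Estimation of Sample Size and Power for Comparing Two Binomial Proportions". No formula is printed.

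The section then allows for dropout. In words, "it is anticipated that about one-twentieth of subjects overall may withdraw from the study prior to completion". In the calculation, the rate entered is 0.083, which gives 31.62, "rounded to 32 subjects per procedure group". The stated purpose is that "sufficient numbers remains at the end of the trial (29 subjects per group" and that this number supports valid conclusions.

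Under *Statistical Analysis*, the first primary analysis is Fisher's exact test, "to compare the proportion of success between the test and the control groups, considering that randomization has been diligently conducted". Under *Statistical Methods*, "Efficacy analysis will be according to the intent to treat (ITT) principle by last observation carried forward (LOCF", and a per-protocol analysis is planned as well.

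**The concern.** A stated power should belong to the test that will be run. Fisher's exact test is conservative in small samples: its true type I error lies well below the nominal 5%, and it loses power accordingly. A sample size taken from an uncorrected approximation therefore overstates what Fisher's test can deliver.

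At stake is the accuracy of a figure that the plan uses to justify its size. If 29 per group were analysed, the chance of missing the assumed effect would be about 29%, not the 20% that a reader would take from the text. The two dropout rates add a second problem, because the enrolment of 32 does not follow from the rate given in words.

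**Working it through.** **Inputs.** From *Rationale for sample size*: p1 = 0.55, p2 = 0.20, two-sided alpha = 0.05, power = 0.80, 29 per group, 32 enrolled per group, dropout one-twentieth (words) and 0.083 (calculation). From *Statistical Analysis*: Fisher's exact test.

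**Step 1: reproduce the 29.** The mean rate is (0.55 + 0.20)/2 = 0.375 and the difference is 0.35.

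- Normal approximation, no continuity correction: n = [1.96·√(2·0.375·0.625) + 0.8416·√(0.55·0.45 + 0.20·0.80)]² / 0.35² = 28.83, so 29. This matches the plan.
- Arcsine approximation: h = 2·asin(√0.55) − 2·asin(√0.20), n = 2·[(1.96 + 0.8416)/h]² = 28.38, so 29. This also matches.
- Normal approximation with continuity correction: 34.30, so 35. This does not match.

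The plan's 29 therefore comes from a method without the allowance that Fisher's test needs.

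**Step 2: power of the planned test.** For each pair of group sizes, take every possible 2×2 table, compute the two-sided Fisher p-value, and add up the binomial probabilities (0.55 and 0.20) of the tables with p ≤ 0.05.

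| Per group (equal) | Fisher power |
|---|---|
| 29 | 71.3% |
| 30 | 73.8% |
| 31 | 76.1% |
| 32 | 78.3% |
| 33 | 80.0% |

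Shortfall from 80%: 80 − 71.3 = 8.7 points at 29, and 80 − 78.3 = 1.7 points at 32. The cause is the test's true size, at most 2.5% at 29/29 and 3.3% at 32/32 (largest value over a grid of 999 common success rates).

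**Step 3: allow for discreteness.** Fisher power jumps with small changes in the split (active/control):

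- 31/32 gives 81.8%, 32/31 gives 80.1%, 32/30 gives 81.0%, 31/33 gives 80.1%.
- Of the 16 splits with 29 to 32 per group, 13 fall below 80% (range 71.3% to 81.8%, mean 77.7%).
- The nine splits with 28 to 30 per group average 74.6%; the nine with 31 to 33 average 80.5%.

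The gap around 29 survives this averaging. Around 32 it largely disappears.

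**Step 4: sensitivity to the assumed rates.**

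| Test vs placebo | 32/32 | 29/29 |
|---|---|---|
| 56% vs 20% | 80.7% | 73.9% |
| 54% vs 20% | 75.8% | 68.7% |
| 55% vs 19% | 81.1% | 74.6% |
| 55% vs 21% | 75.4% | 68.0% |

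A one-point change in either rate moves power across 80% at 32 per group, but never brings it near 80% at 29.

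**Step 5: dropout.** One-twentieth gives 29/0.95 = 30.53, so 31 per group. The 0.083 actually used gives 29/0.917 = 31.62, so 32 per group.

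**The case against.** The strongest reply is that the primary analysis is hardly affected. It is intent-to-treat with the last observation carried forward, and pain is rated after each of the first 11 procedures as well as at the endpoint, so nearly everyone treated will have a value. At 32 per group the shortfall is 1.7 points, less than the movement caused by a one-point change in success rates that the plan gives only as approximate. The equal-split figure of 78.3% is also partly an accident of discreteness: 33/31, with the same total of 64, gives 82.9%, and variable blocks within site do not guarantee an exact 32/32 split. The plan makes no separate power claim for the per-protocol set.

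All of that stands, and it limits the weight of the point. It does not rescue the statement about 29 per group, which the section presents both as the number giving power 0.8 and as the number that suffices at the end of the trial.

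A further reply is that overall study success is defined as a difference of at least 35% between groups. If that means an observed difference, the chance of meeting it at the assumed rates is only about 47% (46.5% at 29 per group, 47.2% at 32), and the choice of test makes no difference to it. That is a separate problem; it does not make 0.8 the power of Fisher's test at 29 per group.

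**Conclusion.** The point holds. At 55% versus 20% and two-sided 0.05, 29 per group gives Fisher power of 71.3%, about 9 points below the stated 0.8. At the enrolled 32 per group the figure is 78.3%, and across nearby splits it is close to 80%. The trial is not materially underpowered for its primary set, provided that set stays near 32 per group; the larger gap matters if numbers fall to 29, as they could per protocol. The dropout rates contradict each other, though the effect is one subject per group.

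These figures rest on the plan's own rates and on two-sided testing, which it states. This is a correction to the sample size text. It is not an argument against Fisher's test or for a larger trial.

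**What to change.** **Needed.** In *Rationale for sample size*, state the power for the planned two-sided Fisher's exact test: about 78% at 32 per group and about 71% at 29, noting that small imbalances move it by a few points. Remove the statement that 29 per group is sufficient for 80%. Use one dropout rate in both the words and the calculation. This is a wording change, with no extra subjects and no change of test.

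**Optional, only if fixed before unblinding.** Pre-specify Boschloo's exact test at two-sided 0.05 in place of Fisher's. It gives 83.7% at 32/32 and 79.6% at 29/29, with maximum size of 4.7% and 4.8%. The gain is small at some splits: 82.7% against 81.8% at 31/32, and 81.3% against 80.1% at 32/31. The cost is some analysis plan text, simple programming and a less familiar method.

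**Separate, with no bearing on the Fisher power.** Randomization is stratified by site, so site could be added to the planned ANCOVA. With the two listed sites this costs one degree of freedom.
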